### 9.4.2 ANALYSIS OF THE PRIMARY ENDPOINT(S)

Longitudinally measured BIS scores will be modeled using linear mixed effects (LME) regression with the measures at each time point relative to baseline (denoted by  $\Delta$ ) as the response variable and fixed effects for experimental conditions (BRIGHT, AC), time (1-week, 1-month, and 3-months post intervention) and their interaction. Models will include subject-specific random effects to account for correlation among measures obtained from the same subject over time. We will use qq-plots and histograms to investigate the assumption of approximate normality and consider transformations (e.g., log) as needed. We will assess the functional form of time to account for any non-linear temporal trends and consider transformations as needed. Comparisons of the change from baseline to each time point between conditions will be performed using model-based linear contrasts. Data will be disaggregated by age, sex, and race to allow for analysis of each as biological variables.

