### 5.5.2 ANTICIPATED ACCRUAL RATE AND ACCRUAL FEASIBILITY

The anticipated accrual rate over the course of the study is 52 accrued patients over 19 months to have 44 analytic subjects complete the study. This accrual rate includes a 20% attrition due to study withdrawal or development of a clinical event that makes the patient non-evaluable. These estimates are based on pilot data from our single-arm pilot trial of BRIGHT. There are no specific accrual targets based on patient characteristics (sex, age, racial/ethnic group). For the proposed study, we predict an accrual rate of 2.3 subjects/month. We expect a slightly higher rate of accrual for the proposed trial because we have refined and optimized our recruitment strategies and SOP based on valuable lessons related to logistics, timing, and methods of screening that we learned while recruiting for the single-arm trial of BRIGHT. Although we would expect an even higher rate of accrual (e.g. 2.5 subjects/month) simply based on improvements that we have made while optimizing the SOP for recruitment, our proposed accrual rate is tempered slightly by the more stringent inclusion criteria that we will be using for the proposed trial. Although our single-arm pilot study included patients with a Body Image Scale

score >1, we refined our inclusion criteria for the proposed study to use a Body Image Scale score of  $\geq$  10 (a clinically relevant threshold), to allow us to target our intervention more precisely and enhance our ability to evaluate mediation. The revised inclusion criterion is expected to impact recruitment minimally; 91% of patients who accrued to BRIGHT in our pilot study would have been eligible with the new criterion. Accrual for the single-arm pilot averaged 2.2 subjects/month. For the proposed study, we predict an accrual rate of 2.3 subjects/month based on the fact that although we improved our accrual strategy based on our pilot work, we will exclude 10% of previously eligible subjects because of more stringent inclusion criteria. Accruing 2.3 subjects/month, we would reach our goal (n=44) in 19 months

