### 5.5.3 PLANNED SCREENING AND RECRUITMENT STRATEGIES

We will screen for potential participants using the electronic medical record (EMR) for the Head and Neck Tumor Center clinical schedule in collaboration with the HNC clinical team. To screen for study eligibility, the research staff will use the EMR to review clinic schedules for new or returning patients with an appointment who are potentially eligible for the study. These appointments will include both in-person clinic visits to the MUSC Head and Neck Tumor Center or a telemedicine visit with a head and neck oncology provider. Clinic rosters will be reviewed at a minimum of once per week, or more frequently if indicated by changes to the clinic schedule. As such, screening will generally be performed within 7 days of enrollment. After a patient who is potentially eligible for the study is identified, the patient will be contacted during the previously identified in-person clinic visit within the MUSC Head and Neck Tumor Center or the telemedicine visit with the head and neck oncology provider to discuss participation in the trial. If it becomes clear that further information is needed to determine study eligibility, the patient will be re-screened pending evaluation of the additional information.

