### 9.2 SAMPLE SIZE DETERMINATION

Our primary objective is to compare change in BIS scores from baseline to 1-month intervention between the BRIGHT and AC arms. The primary endpoint is  $\Delta$  in Body Image Scale scores from baseline to 1-month post-intervention. We hypothesize that, compared with patients who receive the AC, patients who receive BRIGHT will have reduced BID as measured by change in BIS scores at 1-month post-intervention relative to baseline. Alternatively, our null hypothesis is that there will be no difference between BRIGHT and AC in terms of improving BID, as measured by change in BIS scores at 1-month post-intervention relative to baseline. All power and sample size calculations were performed using PASS 2008 version 08.0.13. Based on data from our prospective cohort study and single-arm pilot of BRIGHT, we estimate the mean  $\Delta$  in Body Image Scale scores  $\pm$  SD from baseline to 1-month post are  $0.2 \pm 5.9$  and  $4.6 \pm 3.9$  for control and BRIGHT, respectively. This effect size is clinically significant and realistic given results of other psychobehavioral interventions in breast cancer patients with BID. For n=22/arm (proposed sample size), power exceeds 80% for mean difference in change in Body Image Scale scores of at least 3.1 (with SD as large as 4) or mean difference of at least 5.5 (with SD as large as 7) based on two-sided t-test with  $\alpha=0.1$  (**Fig. 4A**). Group sample size of n=22 (AC, BRIGHT) achieved 80.2% power to detect the standardized effect (mean difference in  $\Delta$  Body Image Scale score from baseline to 1-month divided by the pooled SD=5.62) of 0.78 based on the two-sample t-test with two-sided  $\alpha=0.1$  (**Fig 4B**). We will have greater than 90% power for a standardized effect size of 0.93 and greater than 80% power for a standardized effect size of 0.78. These are both considered moderate effect sizes and are feasible for continuous outcomes in the context of variables that are expected to be modulated by the cancer experience. Our power estimate is conservative given our proposed analysis plan using LME regression, which borrows strength over time and is generally more efficient than a t-test. As such we anticipate that smaller effect sizes than described above will be detectable. Our selection of relaxed significance ( $\alpha = 0.1$ ) with maintained power ( $1 - \beta = 0.8$ ) is based on the desire to emphasize power over type I error at this

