## 9.4 STATISTICAL ANALYSES

### 9.4.1 GENERAL APPROACH

Graphical displays such as scatterplots and boxplots will be constructed to demonstrate patterns of individual continuous measures and differences between baseline, 1-week, 1- and 3-months post intervention. Summary descriptive statistics (e.g. frequencies and percent for categorical variables, and mean, median, standard deviation, and range for continuous variables) will be reported. For inferential tests, we will use a p-value of 0.05, two-sided, and 95% confidence intervals (CIs) to assess statistical significance (Type I error). Covariates will be pre-specified as described below. Normality of the data will be assessed before underlying statistical procedures will be performed. We will evaluate variable transformations as needed to satisfy assumptions and consider transformations of variables to induce approximate normality and stabilize variance as needed. Nonparametric tests will be applied when appropriate.

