#### 9.4.5 BASELINE DESCRIPTIVE STATISTICS

**Fig. 5. Exploratory mediator analysis.** Changes in body image coping behavior (Mediator [M1]) are hypothesized to mediate the effect of the intervention (independent variable [IV]) on changes in body image disturbance (dependent variable [DV]).

Baseline characteristics (e.g., demographics, oncologic details, behavioral characteristics) for the BRIGHT and AC arms will be compared and descriptive statistics calculated. Baseline differences between the two groups will be compared using t-tests and chi-square tests, or Wilcoxon rank sum and Fisher's exact tests as appropriate.

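### The primary mixed model for BIS change has no baseline BIS term; adding one is a low-cost precision refinement, not the repair of an error

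*Combined protocol and SAP*

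**What the plan says.** Section 9.4.2 models BIS at each visit relative to baseline "as the response variable and fixed effects for experimental conditions (BRIGHT, AC), time (1-week, 1-month, and 3-months post intervention) and their interaction", with subject-specific random effects. Baseline BIS is not among the fixed effects. Section 9.4.3 uses the same form for the well-being scales.

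Section 9.4.1 says "Covariates will be pre-specified as described below", but neither 9.4.2 nor 9.4.3 names an adjustment covariate. The covariate list in 8.1 contains the ASI-R, demographics and clinical characteristics, not baseline BIS. Age, sex and race do have a role, as subgroup or moderator variables (9.4.2, 9.4.3, 9.4.7). Section 9.4.5 states that "Baseline differences between the two groups will be compared using t-tests and chi-square tests" and attaches no consequence for the primary model.

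A BIS score of at least 10 is required for entry (5.1, 8.1), so a pre-randomization score exists for everyone. The schedule in 1.3 marks the only pre-treatment BIS in the pre-screen column (day -60 to 1), and 5.5.3 adds "As such, screening will generally be performed within 7 days of enrollment". Elsewhere (2.1, 9.2) the plan speaks of assessments at baseline without saying whether the screening score is that baseline.

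Section 9.2 bases power on an unadjusted t-test of change and then says "Our power estimate is conservative given our proposed analysis plan using LME regression". Its reason is that the model borrows strength over time. It continues: "As such we anticipate that smaller effect sizes than described above will be detectable".

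**The concern.** Analysing change with no baseline term fixes the slope of follow-up on baseline at 1. If the true slope is lower, subtracting baseline one-for-one over-corrects a chance difference between arms, and variation that baseline could explain stays in the residual. A slope below 1 is plausible because the BIS carries measurement error and weeks to months separate the scores.

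With 22 patients per arm, chance imbalance is ordinary. The trial is also meant to guide and power a larger one, so the precision of its 1-month estimate matters. A baseline term fixed in advance would also settle how any BIS difference seen in the 9.4.5 comparisons is handled.

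**Working it through.** **Inputs from 9.2 and 9.4.1.** 22 per arm; mean change 4.6 (BRIGHT) and 0.2 (control), difference 4.4; pooled SD of change 5.62; standardized effect 0.78; alpha 0.10 in 9.2. Section 9.4.1 instead says "we will use a p-value of 0.05, two-sided". That conflict is a separate matter, so both levels are shown.

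**Assumed, not in the documents.** Slope b of 1-month BIS on baseline BIS, 0.3 to 1.0; baseline SD s among those enrolled, 3 to 5. The change SD is held at 5.62.

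**1. The plan's own figure.** Noncentral t, 42 df, noncentrality 0.78 × √(22/2) = 2.59. Power is 81.6% at alpha 0.10, against 80.2% stated, and 71.5% at alpha 0.05. The stated power is reproduced to within two points.

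**2. Variance ratio, adjusted to unadjusted.**

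Ratio = [1 − (1 − b)² s² / 5.62²] × [1 + 1/(2n − 4)]

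With n = 22 the second factor is 1 + 1/40 = 1.025, the price of estimating the slope. For b = 0.5 and s = 4: (0.25 × 16)/31.58 = 0.127, and 0.873 × 1.025 = 0.895. Adjusted power uses 41 df.

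| Slope (s = 4) | Variance ratio | Power, alpha 0.10 | Power, alpha 0.05 |
|---|---|---|---|
| Unadjusted | 1 | 81.6% | 71.5% |
| 0.3 | 0.771 | 89.5% | 82.1% |
| 0.5 | 0.895 | 85.2% | 76.1% |
| 0.7 | 0.978 | 82.3% | 72.4% |
| 0.9 | 1.020 | 80.9% | 70.6% |
| 1.0 | 1.025 | 80.7% | 70.4% |

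At slope 0.5, s of 3 to 5 gives 5% to 18% lower variance.

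**3. Break-even.** The ratio is 1 when (1 − b)² s²/5.62² = 1 − 1/1.025 = 1/41, so 1 − b = 0.156 × 5.62/s. The break-even slope is 0.71, 0.78 and 0.82 at s = 3, 4 and 5.

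**4. How plausible the top row is.** At b = 0.3 and s = 4, the variance of follow-up BIS is 31.58 − (0.7 × 4)² + (0.3 × 4)² = 31.58 − 7.84 + 1.44 = 25.18, so its SD is 5.02. The implied correlation is 1.2/5.02 = 0.24, which is low for repeat scores on one scale. The rows at 0.5 and 0.7 are the better guide.

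**5. The entry cut.** Under a linear relation, selecting on baseline leaves the slope unchanged: in a check with true slope 0.50, it was 0.50 before and after a cut at 10. The cut narrows s and so reduces the gain. Simulations with baseline restricted to 10–30 gave ratios of about 0.85 to 0.98 and adjusted power of 82% to 87% at alpha 0.10. Both analyses were unbiased and held their type I error.

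**6. Chance imbalance.** At s = 4 one standard error of the baseline difference is 4 × √(2/22) = 1.2 points. It moves the unadjusted estimate by (1 − b) × 1.2, that is 0.60 at slope 0.5 and 0.36 at slope 0.7, against a planned 4.4.

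**7. Whether the mixed model already does this.** With complete data and categorical time, the 1-month contrast equalled the raw difference in mean change to within rounding error. The random effect does not stand in for baseline. Pooling residual variance over three visits (42 to 126 df) moves power only from 81.6% to 82.3%. With baseline BIS by time added, the contrast equals a 1-month analysis of covariance.

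**The case against.** Four points on the other side carry weight.

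- **The gain is not established.** A slope below 1 is not enough; it must be below about 0.7 to 0.8, and the documents give no slope or baseline SD. At s = 4 and slope 0.8 the ratio is 1.004. This stands: the omission is certain, the size of the benefit is not.
- **The change is not just a matter of wording.** Section 9.2 cites interim accrual data, the trial is open-label (4.1), and the principal investigator reviews endpoint data monthly (10.1.6). Altering the primary contrast now needs ethics approval and a record that results by arm were not seen. This stands and is part of the cost.
- **The sentence in 9.2 is hedged.** The mixed model does help when 1-month values are missing, which 9.2 anticipates, or when time has a parametric form, which 9.4.2 leaves open. This stands, so the point about 9.2 is secondary.
- **The 9.4.5 comparisons are descriptive.** Nothing says that they trigger adjustment. A post hoc choice is a possibility, not a plan.

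A reader might also infer that entry at BIS of at least 10 biases the comparison through regression to the mean, or that the cut itself pushes the slope below 1. Neither holds. Regression to the mean affects both randomized arms alike, and the cut only narrows the baseline range. Section 5.5.2 reports that "91% of patients who accrued to BRIGHT in our pilot study would have been eligible with the new criterion", which suggests that few are removed, but that comes from a small pilot.

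**Conclusion.** The primary model omits baseline BIS, and no other section supplies it. The planned contrast remains unbiased and meets the stated power at alpha 0.10, so the documents do not support calling this an error or a threat to validity. Nor do they support calling the plan silent on covariates: age, sex and race have stated roles, though not as adjustment terms.

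The likely gain is modest: about 2% to 10% lower variance at slopes 0.7 to 0.5 with an assumed baseline SD of 4. There is none between the break-even slope and 1, and the loss is capped at about 2.5% of variance and 0.9 points of power. The 23% reduction at slope 0.3 should not be quoted as expected. The change is worth making because the possible gain exceeds the capped loss over much of the assumed range and the data are already collected.

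**What to change.** - **Section 9.4.2:** keep change in BIS as the response, add baseline BIS and baseline BIS by time as fixed covariates, and name the baseline-adjusted 1-month arm contrast as primary. Report the unadjusted contrast as a sensitivity analysis.
- **Section 9.4.3:** do the same with each measure's own baseline.
- **Sections 1.3 and 8.1:** state which pre-randomization BIS is the baseline.
- **Section 9.2 (optional):** limit the sentence on conservative power to the settings where the mixed model gains over the t-test, mainly missing 1-month values or a parametric form of time.

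The cost is a few lines of text, no new data, and a documented, ethics-approved amendment made before any look at outcomes by arm.

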### 9.4.3 ANALYSIS OF THE SECONDARY ENDPOINT(S)

For secondary endpoints related to psychological, emotional, and social well-being, graphical displays such as scatterplots and boxplots will be constructed to demonstrate patterns of individual continuous measures and differences between baseline, 1-week, 1- and 3-months post intervention. Summary descriptive statistics (statistics (e.g. frequencies and percent for categorical variables, and mean, median, standard deviation, and range for continuous variables) will be reported. Longitudinal measures of psychological, social, and emotional well-being will be modeled using LME regression with the measures at each time point relative to baseline (denoted by  $\Delta$ ) as the response variable and fixed effects for experimental conditions (BRIGHT, AC), time (1-week, 1-month, and 3-months post intervention) and their interaction. Models will include subject-specific random effects to account for correlation among measures obtained from the same subject over time. We will use qq-plots and histograms to investigate the assumption of approximate normality and consider transformations (e.g., log) as needed. We will assess the functional form of time to account for any non-linear temporal trends and consider transformations as needed. Comparisons of the change from baseline to each time point between

conditions will be performed using model-based linear contrasts. Data will be disaggregated by age, sex, and race to allow for analysis of each as biological variables.

[figure not shown]
To evaluate whether the effect of BRIGHT on change in BID at 1-month post-intervention is partially mediated by changes in body image coping behavior at 1-week post intervention, we will perform exploratory mediation analysis. The total effect of the intervention (path  $c$ ) will be partitioned into direct (path  $c'$ ) and indirect effects, which we will test for statistical significance (Fig. 5). We will examine the direct effect of the intervention on change in BID ( $\Delta$  in Body Image Scale score) the mediating effect of change in body image coping behavior ( $\Delta$  in Body Image Coping Strategies Inventory score) on change in BID, and the effect of the intervention on the mediator ( $\Delta$  in Body Image Coping Strategies Inventory score). If paths  $a$ ,  $b$ , and  $c$  are statistically significant and  $c'$  (the direct effect) is reduced compared with  $c$  (the total effect), then partial mediation criteria are satisfied. The significance of the mediating effect will be tested using robust bootstrapping. Bootstrapping is considered superior to other methods of analyzing indirect effects because bootstrapping provides confidence intervals based on the bootstrap distribution instead of simply p values. In situations with smaller samples and non-normal distributions, the bootstrapping method is more likely to achieve an unbiased estimate of the indirect effect than other methods. The confidence interval for the mediating effect will be provided from the bootstrap analysis with the 'robmed' R package. This analysis will be repeated for change in BID at 3-months post and change in image coping behavior at 1-month post-intervention. Plots of mediated effect will be made to investigate the distribution of data and improve understanding of the relations among the variables. LME regression will be considered to assess the three-way interaction (moderator-intervention-time) for age, sex and race.

For secondary endpoints related to the feasibility and acceptability objectives, simple frequencies will characterize participant satisfaction with the following aspects of the intervention: timing, method of delivery, number of sessions, content relevance, homework utility, attentiveness of the study psychologist, overall satisfaction, and likelihood to recommend BRIGHT. Descriptive statistics will be presented. Our interdisciplinary team will meet after completion of study data analyses to interpret the implications of these findings for how to refine BRIGHT based on these data in preparation for our future large-scale trial.

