#### *Covariates*

Appearance Schemas Inventory-Revised (ASI-R) Score. The ASI-R is a psychometrically sound, 20-item measure of image investment. The ASI-R consists of two subdomains: Self-Evaluative Salience (of Appearance) and Motivational Salience (of Appearance). Items are scored using a 5-point Likert scale from 'strongly disagree' 'strongly agree' (1-5). Items 1, 4, 5, 9, 11, 12 are reverse scored. The composite ASI-R score is calculated as the mean of the 20 items, and thus composite ASI-R scores range from 1-5. The score for each subscale is also calculated as the mean of its included items. Higher scores reflect greater levels of image investment.

The individual's medical chart will be used to collect information performed as part of an individual's regular medical care are going to be used as a part of collection of trial data. As such, Health Insurance Portability and Accountability Act (HIPAA) rules, other relevant federal or state laws, and local institutional requirements will be followed, as applicable. The following information is to be obtained through review of existing data:

Demographics. Demographic characteristics include age, race, ethnicity, sex, marital status, living situation, insurance.

Clinical and Oncologic Characteristics. Clinical characteristics will include body mass index (BMI), comorbid medical conditions, and cancer history. Oncologic characteristics will include HNC tumor subsite, HNC tumor histology, American Joint Committee on Cancer TNM Class and overall stage grouping, type of ablative surgical, type of reconstruction, adjuvant radiation dose, adjuvant chemotherapy dose and agent, and time since completion of treatment.

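### The exploratory mediation models use change in BICSI and change in BIS without baseline terms, which costs power on the randomised paths and leaves path b open to a baseline artefact

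*Combined protocol and SAP*

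**What the plan says.** Section 9.4.3 sets out the mediation analysis: "we will perform exploratory mediation analysis". The outcome is change in BIS at 1 month and the mediator is change in BICSI at 1 week. The section estimates "the effect of the intervention on the mediator" (path a), "the mediating effect of change in body image coping behavior" on the outcome (path b), the total effect (path c) and the direct effect (c'). If a, b and c are significant and c' is smaller than c, "then partial mediation criteria are satisfied". The interval for the indirect effect "will be provided from the bootstrap analysis with the 'robmed' R package". A second model follows: "This analysis will be repeated for change in BID at 3-months post and change in image coping behavior at 1-month post-intervention".

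No covariate is named for any of these models. Section 9.4.1 says "Covariates will be pre-specified as described below", but Sections 9.4.1 to 9.4.3 contain no list. The Covariates heading in Section 8.1 covers the ASI-R, demographics and clinical history, not baseline BICSI or BIS.

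Both baselines exist. The schedule in Section 1.3 places BICSI at Visit 1 and BIS at pre-screening.

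**The concern.** Randomisation protects paths a and c. For these, leaving out the baseline is a matter of efficiency: a raw change score carries the noise of two measurements.

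Path b is different, because nobody is randomised to a level of coping. Each change score contains its own baseline. Section 8.1 itself says that avoidance and appearance fixing go with more body image disturbance, and positive rational acceptance with less. If the two baselines are correlated and both measures regress towards their means, the two changes move together even when coping has no effect on BIS. If BRIGHT also shifts BICSI, as the protocol expects, that association becomes a false indirect effect.

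At stake is the mechanism claim. The synopsis and Section 4.1 put partial mediation by coping among the main hypotheses, and Section 9.4.3 sets a pass/fail rule for it. The primary endpoint analysis is not affected.

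**Working it through.** **The plan's own figure.** The documents give no power or error rate for the mediation analysis. The only related figure is in Section 9.2: 80.2% power for a standardised effect of 0.78, 22 per arm, two-sided alpha 0.1. The noncentral t with 42 degrees of freedom and noncentrality 0.78 × √(22/2) = 2.59 gives 81.6%, close to the stated value.

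**Inputs.** From the documents: 22 per arm, 1:1 allocation, two-sided 0.05 for inferential tests (Section 9.4.1), and the a/b/c/c' rule. Assumed, because the documents do not give them: correlation r between baseline BICSI and baseline BIS; correlation ρ between baseline and follow-up of the same measure; an effect of about 0.8 SD on each measure; equal SDs at both times. The true effect of coping on BIS is set to zero.

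**Step 1: power for path a.** The SD of a change score is √(2(1 − ρ)). After adjustment for the measure's own baseline it is √(1 − ρ²).

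| ρ | Effect ÷ SD, change score | Power | Effect ÷ SD, adjusted | Power |
|---|---|---|---|---|
| 0.3 | 0.8 / 1.183 = 0.68 | 59% | 0.8 / 0.954 = 0.84 | 77% |
| 0.5 | 0.8 / 1.000 = 0.80 | 74% | 0.8 / 0.866 = 0.92 | 85% |

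These are noncentral t values with 22 per arm and two-sided 0.05. Simulation with both baselines in the model agrees to within 2 points: about 61% to 76% at ρ = 0.3, and 75% to 84% at ρ = 0.5. The same formula applies to path c for an effect of the same size.

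**Step 2: false path b in a lagged model.** Suppose each follow-up depends only on its own baseline plus independent noise. Within an arm:

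- covariance of the two changes = r(1 − ρ)²
- variance of change in BICSI = 2(1 − ρ)
- false b = r(1 − ρ)/2, in SD units
- false indirect effect = 0.8 × r(1 − ρ)/2

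At r = 0.4, ρ = 0.7: 0.8 × 0.4 × 0.3/2 = 0.048 SD. At r = ρ = 0.5: 0.8 × 0.125 = 0.10 SD. At r = 0.6, ρ = 0.3: 0.8 × 0.6 × 0.7/2 = 0.168 SD. With both baselines in the model the value is zero.

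**Step 3: how often the plan's rule would be met.** This was simulated with ordinary least squares in place of the robust bootstrap, 44 patients and no true mediator effect.

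| Setting | Change scores only | Baselines added |
|---|---|---|
| r = ρ = 0.5 | 6.4% | 1.7% |
| r 0.4 to 0.6, ρ 0.3 to 0.7 | about 5 to 10% | about 1 to 2% |
| r 0.3 to 0.7, ρ 0.3 to 0.7 | 3.5 to 12.7% | 1.2 to 2.2% |

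At r = ρ = 0.5 with 1,000 patients, the false effect stays at 0.10 SD and the rule is met in 98% of trials, so this is bias and not small-sample noise. Two things reduce it. If BRIGHT does not change BICSI, the rule is met in at most 0.4% of trials. If baseline BIS is truncated from below, in the manner of the entry criterion of BIS at least 10, the false effect at r = ρ = 0.5 falls to 0.03 to 0.05 SD.

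**Step 4: other data-generating models.** Suppose instead that the correlation comes only from stable traits, each measured with independent noise. All four cross-correlations between the measures then equal r, so the covariance of the changes is r − r − r + r = 0 and the change-score model is unbiased. Adjusting for the noisy baselines now introduces a false indirect effect: about 0.05 SD at stability 0.7 and r = 0.3, and about 0.20 SD at stability 0.5 and r = 0.5. If day-to-day states are also correlated, both models are biased and adjustment only reduces the error, for example from 0.20 to 0.13 SD at stability 0.5 and r = 0.5.

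**The case against.** The strongest objection is that the choice between change scores and baseline adjustment for a non-randomised mediator is contested, and the documents give nothing that would settle it. The lagged model is one assumption among several. It implies that the within-arm correlation of coping and BIS falls from r to ρ²r at follow-up, for example from 0.6 to 0.09 × 0.6 = 0.05 when ρ = 0.3. Section 8.1 describes a general association, not one that almost vanishes within weeks. All of this stands. A reader might infer that adjustment removes the bias in general; Step 4 shows that it does not.

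A reader might also take the false-positive rate of path b alone, about 7 to 27% under the lagged model, as the chance of a false mechanism claim. The plan requires a, b and c all to be significant and c' to be smaller than c, so the figures in Step 3 are the relevant ones.

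Three further inferences go too far. The plan is silent on baseline adjustment; it does not rule it out. The ASI-R is described as "The ASI-R is a psychometrically sound, 20-item measure of image investment", but nothing in the documents shows that it confounds path b, so its absence from these models is not a fault. Finally, the analysis is labelled exploratory in a pilot trial, which limits the consequence. That label does not remove the need to specify the models, since the plan attaches a decision rule to them.

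The power gain on paths a and c does not depend on this dispute. Arm is randomised, and adjustment gained power under every model examined.

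**Conclusion.** The point holds in two parts. On the randomised paths, leaving out baselines that are already collected gives up power: about 15 points for path a at ρ = 0.3 (61% to 76%) and 9 points at ρ = 0.5 (75% to 84%), for an assumed effect of 0.8 SD. On path b, the change-score model is open to a false indirect effect of about 0.05 to 0.17 SD under a lagged model with r from 0.4 to 0.6 and ρ from 0.3 to 0.7, with the full rule met in about 5 to 10% of trials against 1 to 2% adjusted.

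The second part is conditional. It needs correlated baselines, regression to the mean and an effect of BRIGHT on BICSI. It can vanish or reverse under a stable-trait model. Neither analysis of path b is safe alone, and the plan does not say which it will use or what it assumes. The robust bootstrap itself was not simulated.

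**What to change.** In Section 9.4.3:

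1. Include baseline BICSI (the subscale used as mediator, to be named) and baseline BIS (identified as the pre-screening score if that is what is meant) as covariates in the mediator, total-effect and outcome models, at 1 month and in the 3-month repeat.
2. Report the unadjusted change-score model as a pre-specified sensitivity analysis.
3. State that path b assumes no unmeasured confounding between change in coping and change in BIS.
4. Claim mediation only if the adjusted and unadjusted versions agree.

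The cost is two degrees of freedom in each model, one extra analysis and a few lines of text. No new data are needed.
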